4.3. Inclusion Criteria

Household members who meet all of the following criteria are eligible for enrollment as study participants:

- a. The index participant and/or caregiver understands the study procedures, is willing to conduct them at home, and has the ability to use either a computer or a smart phone to link to and respond to the study questionnaires. If the family does not have access to a computer or a smart phone, they are willing to speak with a study member to answer the questionnaires.
- b. The index participant is 21 years old and younger, lives with caregiver(s), and is or has been a participant in a NIH-funded clinical study from which information on respiratory conditions, including asthma, and other atopic and allergic diseases is available.
- c. The index participant and caregiver will reside in the United States, including Puerto Rico, for the duration of the study.
- d. The index participant will live with the caregiver for at least 50% of the time for the duration of the study.
- e. An English or Spanish speaker is available to serve as the primary contact and as the person who will be responsible for the completion of questionnaires and the collection of study biological samples.
- f. Qualifying siblings must be under 21 years of age and live in the same home as the index participant and caregiver.

4.4. Exclusion Criteria

Individuals who meet any of the following criteria are not eligible for enrollment as study participants:

Past or current medical problems, which, in the opinion of the site investigator, may pose risks from participation in the study, may interfere with the participant's ability to comply with study requirements or may impact the quality or interpretation of the data obtained from the study

5. Known and Potential Risks and Benefits to Participants

5.1 Risks of Study Procedures

5.1.1 Nasal Swabs and Nasal Secretions

- a. Nasal swab and nasal secretion collection may cause localized discomfort. Rarely, mild epistaxis may occur.
- b. There is a risk of irritation if the liquid reagent in the nasal swab collection kit comes in contact with the skin. Gloves will be provided to reduce the risk of skin contact.
- c. Risk of infection: It is unknown whether the collection of the biospecimens outlined in this protocol increases the risk of infection to household members beyond that of living in the same household with study participants. There is a distinction between what should be expected in a healthcare setting and the home. In this respect, home collection probably does not merit use of the level of personal protective equipment (PPE) recommended for healthcare workers. Because it is not known whether the collection of the biospecimens outlined in this protocol increases the risk of infection to household members beyond that of living in the same household with study participants, we include viral transmission as a potential risk of study participation. Because we do not know if there is an increased risk of infection transmission, as a precaution, the study will provide, recommend, and teach proper use of barrier protection to those assisting with biospecimen collection (collection of anterior nasal swab in age 10 and under, inferior turbinate swab for age 11+, stool swab, capillary blood collection).

Personal Protective Equipment (PPE) plan: The proposed PPE plan for this study is based on available data and guidance from the CDC at the time the study was implemented to prevent any significant additional infectious risk to the family members performing the swabs given both the nature of the procedure being non-aerosol generating and the ongoing level of contact within the household.

1. **Masks.** We recognize that the CDC at the time of writing of this protocol does still recommend use of an N95 or higher-level respirator during collection of a nasopharyngeal (NP) sample for SARS-CoV-2 testing by healthcare providers. However, there are no recommendations for collection by household members nor any recommendations for collecting anterior nares and mid-length, inferior turbinate samples. The CDC guidance does acknowledge that not all procedures are equally likely to generate infectious aerosols and that NP swabs therefore would be a lower priority for use of N95 masks than more invasive procedures such as intubation, if availability of N95 masks is limited. The collection of anterior nares swabs and inferior turbinate swabs, which are proposed to be performed in this study, is less likely to induce coughing and possible aerosol generation compared with NP swabs, although even NP swabs are not considered AGP. Thus, we believe that there is lesser utility of an N95 in the setting of such sample collection. In addition, an

N95 mask cannot be fit tested in this scenario, and without fit testing there isn't any assurance that an N95 mask will provide any better protection than a surgical mask.

2. **Other barrier protection:** The CDC guidance for specimen collection by healthcare providers also specifies the use of a gown in addition to the PPE we are recommending. We do not view a gown in the home as necessary given the differences between the healthcare and home environments. When family members have physical contact with the child throughout the rest of the day without such a barrier, the benefit of the gown is questionable. We are recommending gloves for the dual purpose of barrier protection and protection from inadvertent contact with the liquid reagent provided in the tubes into which the swabs will be placed, as the liquid reagent may cause mild irritation of the skin.
3. **Ethical use of PPE:** At the time of development of this protocol, PPE shortages, including N95 masks are currently (March – April 2020) posing a tremendous challenge to the US healthcare system because of the COVID-19 pandemic. Healthcare facilities are having difficulty accessing the needed PPE and are having to identify alternate ways to provide patient care. There is an Emergency Use Authorization (EUA) of Respiratory Protective Devices; on February 4, 2020, the HHS Secretary declared that circumstances exist to justify the authorization of emergency use of additional respiratory protective devices in healthcare settings during the COVID-19 outbreak. Thus, recommending PPE for this protocol in excess of what has been included and in the absence of any likely benefit would not be responsible use of limited resources and could not be endorsed.

Summary: In summary, it is unknown whether the collection of the biospecimens outlined in this protocol increases the risk of infection to household members beyond that of living in the same household with study participants. Because of this uncertainty, viral transmission is included as a potential risk of study participation, and a barrier protection plan is recommended. However, the collection of these samples by household members does not merit use of the level of PPE recommended for healthcare workers. Thus, use of a surgical mask, eye shield, gloves, and education on proper use, in addition to hand hygiene, are deemed to provide protection for household members assisting with biospecimen collection. These recommendations were developed based on there being a clear distinction between what should be expected in a healthcare setting and the home, and the procedures being conducted. It is not known whether our recommendation of barrier protection precautions for those living in the same household who assist with biospecimen collection are even necessary, but the benefits seem plausible, and the harms unlikely.

5.1.2 Blood Collection

The risks associated with drawing blood via the OnDemand device include syncope, local discomfort where the lancet is inserted, and, in rare cases, local infection. Participants are instructed to remain seated while using the OnDemand device and during blood collection and to lay down if a participant feels light-headed or experiences dizziness. Universal precautions will be followed to reduce the risk of infection.

5.1.3. Stool and Saliva Collections

There are no significant risks associated with saliva sample collection.

There is a risk of irritation if the liquid reagent in the stool swab collection kit comes in contact with the skin. Gloves will be provided to reduce the risk of skin contact.

5.1.4. Questionnaires/Surveys

There is a possibility that participants may find questions too personal. Participants may refuse to answer any questions that make them feel uncomfortable. Participants will provide name, address, phone number, and date of birth. This information will be shared with the sponsor (NIAID/DAIT), the Data Management Coordinating Center (DMCC) at Vanderbilt University, the company that is sending the sample kits to the participants home, and the researchers and staff that are part of this study.

5.1.5. Breach of Confidentiality

As in every research study, unauthorized access to identified data is a risk. The REDCap data system into which participants will directly enter personal data is an established data system that provides several levels of security.

5.2. Potential Benefits

This study will provide no direct benefit for participants. The public health benefit for this study is to collect data regarding incidence of symptomatic and asymptomatic SARS-CoV-2 in a large convenience sample in order to inform decisions regarding interventions to control spread of SARS-CoV-2 infection and possibly design proactive interventions to prevent future COVID-19 outbreaks. This study will provide timely and useful evidence and may enable public health authorities to be more effective in their efforts to protect and promote public health related to SARS-CoV-2.

6. Study Procedures

6.1. Enrollment and Training

Potential study participants (usually the primary care provider for minor children) will be contacted by a member of the clinical research site staff via text, email, or phone call who will direct them to the link to the study HEROS home web page. If interested in participating in the study, the participant/caregiver will be given instructions to view the study web portal. The potential participant will read an information sheet that includes details about the study, study requirements, and study risks, and will provide assurance that each participating family member has read the information sheet and agrees to participate for themselves, index participants, and other family members. The participant will then be directed to complete an electronic registration form and to complete a baseline questionnaire. Once this process is completed, the participant is considered enrolled in the study and will be assigned a unique participant number. All participating family members will be assigned unique participant numbers. Upon completion of these tasks, the sample kit distribution center will mail each household a set of sample collection kits for initiation of bio-sampling.

Once enrolled, the primary contact/caregiver and each participant will be requested to undergo a web-based training that will describe in detail the processes of sample collection and handling. Study staff will be available by phone, Skype, text, or video conferencing for further instructions and clarifications on sample collection procedures.

At Week 18, the primary contact/caregiver will be electronically sent an information sheet that includes details about a study extension that will include collecting 4 additional nasal swabs for a total of 14 nasal swabs over 28 weeks. The information sheet will require that each participating family member attest that they have read the information sheet. The household will have the option to continue with the original visit and sample collection schedule (10 nasal swab collections over 24 weeks), to participate in the study extension with 4 additional nasal swab collections, or to request further information via contact with their local study site.

6.2. Index participants and Household Contacts Study Assessments

6.2.1 Caregiver-Collected Samples

At the times shown in the Schedule of Events (Table A), the primary contact/caregiver will collect nasal swabs from the index participants and all family members that are enrolled in the study at the beginning of the study (Week 2) and every 2 weeks thereafter for 9 collections, then a final 10th nasal swab collected at the end of the study (total 10 nasal swabs collected over 24 weeks). If the household agrees to participate in the study extension, 4 additional nasal swabs will be collected between Week 18 and Week 28 (Table A). Stool samples via swabs will be collected from the index participants and all family members that are enrolled (starting at Week 2) into the study (Table A). Blood samples will be collected via the OnDemand device from the index participants and all family members that are enrolled in the study and 2 years of age and older (Table A). Nasal secretion and/or saliva samples may also be collected from the index participants and all enrolled family members at Week 24. Samples will be shipped as instructed in the sample kit package. Details of the nasal swab, stool collection, blood collection, nasal secretion, and saliva procedures will be provided in the sample kit package.

6.2.2. Questionnaires

At the times shown in the Schedule of Events (Table A), the primary contact/caregiver will have the responsibility to ensure that on-line questionnaires regarding current symptoms and recent exposures will be completed for all participants. A symptom and exposure survey will be completed every 2 weeks starting at Week 2 to coincide with nasal sample collection. A health check survey to detect any illness in the household in the intervening weeks will be completed every 2 weeks starting at Week 1. The caregiver will be instructed on how to access and complete the on-line questionnaires.

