6.4. Sample Collection/Questionnaire Completion Windows

Sample collection and completion of the study questionnaires should take place within the time limits specified in the Schedule of Events (Table A).

Table A. Schedule of Events for All Participants

*The window for sample collection and completion of Symptom and Exposure surveys is (+/-) 4 business days

¹There is no window for the baseline (Week 2) blood collection.

²Additional nasal swab and a stool samples will be collected when a household member shows signs of a viral illness and a study-specified threshold for symptom algorithm has been met. For the first illness, the nasal swab sample will be collected within 24 hours from all study participants, including the affected household member, and a stool sample from just the affected household member. Subsequent illnesses will be assessed only if the index participant is affected; in this case a swab and a stool sample will be obtained within 24 hours only from the index participant.

³A nasal secretion and/or saliva sample may be collected at End of Study.

⁴Nasal swabs will be collected at Week 20, 22, 26 and 28 and Health Check Surveys at Week 19, 21, 23, 25, and 27 from participants that agree to participate in the study extension.

⁵An end of study blood sample will be collected from all study participants that are at least 2 years old at Week 24 or at Week 28, if the participant decided to continue in the study with the original visit plan or agreed to participate in the extension, respectively.

⁶An additional blood sample will be collected from all study participants that are at least 2 years old three weeks after a first illness in the household and a study-specified threshold for the symptom algorithm has been met.

7. Laboratory Assays

- SARS-CoV-2 detection and nasal transcriptomics. RNA extracted from all swabs will be used to perform RT-qPCR for SARS-CoV-2. The remaining RNA and DNA will be stored for possible detection (and quantification) of other respiratory viruses, for generating the host transcriptome response to infection (from airway epithelial and any immune cells that were present on the nasal swab), and for delineating the nasal microbiome at the time the swab was collected.

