11.2 Analysis Plan

Population description

Baseline characteristics of 2000 index children and their families that include age, sex, household members, co-morbidities, proportion with evidence of SARS-CoV-2 infection at baseline, and follow-up will be described using standard statistical techniques such as proportions for categorical variables and means and standard deviations (SD), or medians and interquartile ranges as appropriate.

Primary outcome: The cumulative incidence of SARS-CoV-2 RNA detection in nasal samples among index participants and their household contacts over the study period

Time to event analyses will be conducted among participants that are SARS-CoV-2 serologically negative at entry. We will use Kaplan-Meier cumulative morbidity curves for the primary analysis. The primary endpoint will be calculated at the end of follow-up or fate defined as follows. Follow-up time will be the time from entry until the first of the following events:

- Tests positive for SARS-CoV-2 RNA in nasal samples
- Is lost to follow-up or withdraws from the study
- End of study (24 weeks)

Fate at the end of follow-up will be:

- 1 (positive): if the patient tests positive for SARS-CoV-2.
- 0 (censored): if the patient has no evidence of having had disease by the end of follow-up.

Attack rates

SARS-CoV-2 attack rate per person-week will be calculated. Attack rates within families will also be estimated.

Secondary outcome: time to the index participants and their household members with detectable SARS-CoV-2-specific antibodies in serum over the study period.

Cox regression on seroconversion status at 24 weeks: Hazard ratios will be modeled using Cox Regression to compare demographic and clinical factors to the time to detectable SARS-CoV-2-specific antibodies in serum.

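### Under Table A footnote 4, original-schedule households appear to lose the Week 19, 21 and 23 health checks that Section 6.2.2 read alone gives everyone, inside the 24-week primary window

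*Combined protocol and SAP*

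**What the plan says.** Section 6.2.2 sets two recurring questionnaires. The first follows the swabs: "A symptom and exposure survey will be completed every 2 weeks starting at Week 2 to coincide with nasal sample collection". The second covers the weeks between: "A health check survey to detect any illness in the household in the intervening weeks will be completed every 2 weeks starting at Week 1". Neither sentence gives a last week or separates households by schedule. The section opens, however, by referring timing to the schedule table: "At the times shown in the Schedule of Events (Table A), the primary contact/caregiver will have the responsibility to ensure that on-line questionnaires".

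Footnote 4 to Table A (Section 6.4) lists what the extension involves. Besides swabs at Weeks 20, 22, 26 and 28, it lists "Health Check Surveys at Week 19, 21, 23, 25, and 27 from participants that agree to participate in the study extension".

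The extension is optional and is offered at Week 18. Section 6.1 describes the alternative: "The household will have the option to continue with the original visit and sample collection schedule (10 nasal swab collections over 24 weeks". On that schedule swabbing begins in Week 2, after which Section 6.2.1 specifies: "every 2 weeks thereafter for 9 collections, then a final 10th nasal swab collected at the end of the study (total 10 nasal swabs collected". Section 9.1 keeps these households in the study to Week 24. Section 11.2 ends follow-up for the primary endpoint, absent an earlier positive test or loss, at "End of study (24 weeks)", with no reference to which schedule a household chose.

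**The concern.** The health check exists to find illness in the household between swab weeks. Under Section 6.3.1, a first illness that meets the symptom threshold triggers nasal swabs from every enrolled household member, not only the one who is ill. A prompt that brings an illness to light can therefore also reveal a silent infection in someone else, and silent infection is part of the study's rationale in Section 1.

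Between the Week 18 and Week 24 swabs, an original-schedule household has no routine swab, so an illness-triggered swab is the only way to detect RNA before Week 24. If the health checks stop as well, the prompt disappears just when routine sampling does. It disappears only for households that declined the extension, a group that selects itself. Ascertainment of the primary endpoint would then depend on extension choice in one more respect inside the 24-week window, and Section 11.2 does not address this.

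**Working it through.** **1. Reproduce the plan's swab counts.** Inputs: Sections 6.1 and 6.2.1 and footnote 4.
- Original schedule: Weeks 2, 4, …, 18 give (18 − 2)/2 + 1 = 9 swabs; adding Week 24 gives 10, as stated.
- Extension: adding Weeks 20, 22, 26 and 28 gives 10 + 4 = 14, matching "collecting 4 additional nasal swabs for a total of 14 nasal swabs over 28 weeks".
- The other reading of 6.2.1 (Week 2, then nine more, then a final swab) gives 1 + 9 + 1 = 11 and does not match. Regular two-weekly swabs therefore end at Week 18 on the original schedule.

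**2. Count health checks.** The documents state no total, so there is no figure to reproduce.
- Original schedule, 6.2.2 read alone: Weeks 1, 3, …, 23 give (23 − 1)/2 + 1 = 12.
- Original schedule, footnote 4 applied: Weeks 1, 3, …, 17 give (17 − 1)/2 + 1 = 9.
- Difference: 12 − 9 = 3, at Weeks 19, 21 and 23.
- Extension household: Weeks 1, 3, …, 27 give (27 − 1)/2 + 1 = 14 under either text.

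**3. Is footnote 4 a list of extension-only items?** It does not say so outright, but its swab list suggests it. That list omits Week 24, when every household is swabbed, and names only the added swabs. If the checks at Weeks 19, 21 and 23 were common to all, only Weeks 25 and 27 would need listing.

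**4. Is there any other scheduled contact between the Week 18 and Week 24 swabs?** This depends on the symptom and exposure survey.
- If it follows the swabs, an original-schedule household has no scheduled contact in Weeks 19 to 23. The gap is 24 − 18 = 6 weeks, or 6/24 = 25% of the primary window. At all other times scheduled contacts are one week apart.
- If it is literally two-weekly, surveys remain at Weeks 20 and 22 and the longest gap is 2 weeks.

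The first reading is the more likely. Section 6.2.2 ties this survey to nasal sampling, and Section 3.1 also places these surveys at the time of sample collection. The three health checks are in question under both readings.

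**5. What the swab gap implies, and what it does not.** Suppose RNA stays detectable for D days, infections are spread evenly over the 42 days from Week 18 to Week 24, detectability is immediate and the assay is perfect. The Week 24 swab alone then finds D/42 of infections acquired in the gap:
- D = 7: 7/42 = 17%
- D = 10: 10/42 = 24%
- D = 14: 14/42 = 33%
- D = 21: 21/42 = 50%

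D is an assumption; the documents give no value. These figures describe the planned six-week swab gap. They are not the yield lost by omitting three surveys, which would also require the rate of symptomatic illness, the share that caregivers report unprompted, and the share that meets the symptom threshold. The documents give none of these.

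**The case against.** The strongest reply is that the texts fit together. Section 6.2.2 defers to Table A, footnote 4 belongs to Table A, and 6.2.2 gives no end week. The health check covers the weeks between two-weekly swabs; once those swabs stop at Week 18, stopping the checks too is a coherent design. The body of Table A is not readable in the available text, so it cannot be ruled out that the grid settles the matter. This stands, and a flat contradiction, which a reader might infer, is not established. But if footnote 4 is simply the operative detail, the loss of the prompt is the operative rule.

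A reader might also infer that these households are wholly unprompted, or even unobserved, from Week 18 to Week 24. The documents do not support that. Weeks 18 and 24 each have a swab, footnote 4 says nothing about the symptom survey, and Section 6.3.1 requires caregivers in every household to complete a symptom survey when illness occurs, whatever their extension choice. After a household's first illness event, moreover, Section 6.3.2 investigates only the index participant's illnesses, so the prompt has less to offer there.

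Finally, extension households are swabbed at Weeks 20 and 22 and the others are not. Ascertainment therefore differs within the primary window whatever is done about the surveys. That is correct, and restoring the surveys would not remove it.

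**Conclusion.** The point holds as a matter of scheduling and ascertainment. Three of the 12 health checks that 6.2.2 read alone gives an original-schedule household are assigned by footnote 4 to extension households, and all three fall inside the 24-week primary window. Under footnote 4 there is no health check, and probably no scheduled contact of any kind, between the Week 18 and Week 24 swabs. The word probably rests on the symptom survey following the swabs.

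Only the reminder is lost; caregiver-initiated reporting continues. The effect on cumulative incidence is not quantified and cannot be from these documents, which also do not say how many households stay on the original schedule. It would be wrong to take the 17% to 50% detection figures as the size of this problem, or to conclude that the primary estimate is shown to be biased by the missing surveys. No sample-size or precision figure in Section 11.3 is affected. The change is worth making because it is cheap and puts the prompt back where routine swabbing is absent.

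**What to change.** Reconcile Section 6.2.2 with footnote 4, and check the grid of Table A against both. Limit the footnote's extension wording to the swabs at Weeks 20, 22, 26 and 28 and the health checks at Weeks 25 and 27. The checks at Weeks 19, 21 and 23 then go to every household, as 6.2.2 reads on its own. It would help to state in 6.2.2 the last health check week for each schedule, and whether the symptom and exposure survey is due at Weeks 20 and 22 when no swab is.

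The cost is a text edit and three short online surveys per original-schedule household. The swab difference at Weeks 20 and 22 remains, and the surveys do nothing for an infection in a household where nobody falls ill.

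Censoring original-schedule households at Week 18 is not recommended as a substitute. It would discard their scheduled Week 24 swab and censor a self-selected group.
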